### 1 Overview

### 1.1 Study Rationale and Design

The final stage of dementia is characterized by recurrent suspected infections. Research has shown these episodes are widely mismanaged, leading to adverse patient and public health outcomes. Antimicrobials are extensively prescribed in advanced dementia, most often in the absence of clinical evidence to support a bacterial infection. Antimicrobial exposure is the main risk factor for multidrug-resistant organisms (MDROs). Nursing home (NH) residents with advanced dementia are three times more likely to be colonized with MDROs compared to other residents. Moreover, as these patients are in the terminal phase of dementia, evidence suggests they may not clinically benefit from antimicrobials. Comfort is the stated goal of care for 90% of advanced dementia patients, and the risks and burdens associated with work-up and treatment of suspected infections generally do not promote that goal, particularly when hospitalization is involved. Taken together, there is a clear need to improve infection management in advanced dementia both to provide better end-of-life care to these patients and reduce the public health threat of MDROs.

This is a 52-month study (8 months preparation; 36 months to conduct the trial; 8 months data analyses and manuscript preparation) of a cluster randomized controlled trial (RCT) of an intervention to improve infection management for suspected UTIs and LRIs among residents with advanced dementia (N=410; N=205/arm) living in NHs (N=28; N=14/arm). The NH is the unit of randomization as the intervention must be delivered at the facility level to avoid contamination and because this is how it would be employed in the real-world. Analyses will be at the patient level.

### 1.2 Objectives and Outcomes

The Specific Aims are:

Aim 1. To conduct a cluster RCT of an intervention to improve infection management among 410 residents with advanced dementia (N=205/arm) residing in 28 NHs (N=14/arm) and compare the total number of antimicrobial courses for suspected UTIs and LRIs/person-year (primary outcome) over 12 months in the intervention vs. control (usual care) arms. Data will be obtained from review of the residents' charts and medication administration records q2months up to 12 months.

H1. The number of antimicrobial courses/person-years will be lower in the intervention vs. control arms.

Aim 2. To compare the number of antimicrobial courses prescribed for suspected UTIs and LRIs when minimal criteria for treatment initiation are absent based on consensus guidelines/person-vear (secondary outcome) in the intervention vs. control arm over 12 months.

H2. The number of courses prescribed when minimal criteria are absent /person-year will be lower in the intervention vs. control arm.

Aim 3. To compare the following outcomes in the intervention vs. controls arms over 12 months: i. advance care planning about infection management (e.g., documented discussions between proxies and providers, advance directives to withhold antimicrobials), and ii. number of burdensome procedures used to evaluate suspected LRIs and UTIs (hospital transfer, bladder catheterization, chest x-ray, blood draws)/person-year.

H3a. Advance care planning about infections will be higher in the intervention vs. control arms. H3b. The number of burdensome procedures/person-days will be lower in the intervention vs. control arms.

### 1.3 Inclusion and Exclusion Criteria

Inclusion criteria:

### A. Residents

The eligibility criteria and protocol to identify NH residents with advanced dementia will be similar to those used in the 4 prior R01s and the pilot R21 preceding this trial, which together have identified >2300 such residents. Resident eligibility criteria are: 1) age > or = to 60 years, 2) A diagnosis of dementia (any type), 3) Global Deterioration Scale (GDS) score of 7, 4) NH length of stay >90 days, and 5) an individual who can communicate in English has been formally or informally designated as a health care proxy (95% family members in prior studies). GDS stage 7 features include: profound memory deficits (cannot recognize family), total functional dependence, speech <= 5 words, incontinence, and non-ambulatory.

GDS 7 was chosen to define advanced dementia as it has been successfully operationalized and validated in our prior studies, and experts agreed to use this definition in research studies. A 90-day minimum length of stay was chosen to exclude short-stay patients.

At baseline and q2months for 1 year, a research assistant will interview nurses on each NH unit to identify eligible residents. Eligibility will be confirmed by chart review.

### B. NH Providers in Intervention Nursing Homes

Eligibility criteria for providers in the intervention nursing homes include: a nurse, nurse practitioner, physician or physician assistant identified by a senior administrator as an individual who cares for residents with advanced dementia, able to communicate in English (because intervention materials are all in English), and over 21 years of age.

In partnership with the nursing homes leadership, the TRAIN-AD intervention will be rolled out as a new program within the facility. Within that context, the provider educational component of TRAIN-AD intervention will target the "usual" providers in that nursing home who commonly care for advanced dementia residents, i.e., dedicated employees (e.g.,

nurses) and medical providers with privileges (e.g., physicians, nurse practitioners, physician assistants).

### Exclusion criteria:

Residents with cognitive impairment due to causes other than dementia (e.g., head trauma and in short-term, sub-acute SNFs) will be excluded.

Residents' whose proxies cannot communicate in English will be excluded from the study, because the information directed to proxies are only in English.

Providers that do not provide direct care to residents with advanced dementia or who do not speak English.

### 1.4 Duration of Participation and Duration of Study

This is a 52-month study (8 months preparation, 36 months to conduct the trial and 8 months of data analyses and manuscript preparation. At each participating facility there will be a 3 month start-up period, 12-months resident screening and enrollment and up to 24 months data collection total (12 months follow-up for each resident deemed eligible over the 12 months screening).

### 1.6 Interim Data Safety Reviews

As agreed upon by the NIA and overseeing project officer, [name], safety monitoring will be the responsibility of a Data Safety Monitor (DSM), [name] of the University of Missiouri. The PI will meet with [name] duration the preparation stage of the study via conference call, to provide input and guidance on the study evaluation and intervention protocols, data handling activities, and quality assurance and safety issues. Together they will agree on definitions of adverse events and the content of the regular DSM reports. Once the study starts, the DSM will be sent a report prepared by the research team summarizing the overall study status, recruitment, data completion rates, adverse events, and protocol deviations, and outcomes (only if desired). Data will be presented aggregated for both arms of the RCT, and in a sub-report that the PI will not see, in a semi-blinded fashion with study arms labeled as Group 1 and Group 2.

### 1.7 Interim Analyses and Stopping Rules

The DSM will be free to determine the need to stop the continuation of the study based on examination of data safety and monitoring reports; however, there are no interim analyses or *a priori* stopping rules established for this minimal risk study.

### 1.8 Rationale for Number of Residents

Calculations use two-sided testing, assuming a type I error rate of 5% and 90% power, and adjust for potential dependence of observations within NHs using an intracluster correlation of 0.01 based on data from the Study of Pathogen Resistance and Exposure to Antibiotics in Dementia (SPREAD) study conducted in 35 NHs. Based on SPREAD data, we estimate the total antimicrobial courses/person-year in the control arm will be  $\sim$ 1.26, of which 72% (0.91 courses/person-year) will not meet minimal criteria for treatment. Based on prior work, we estimate that we can reduce the % of courses not meeting minimal criteria in the intervention arm by 35%, for a reduction in total courses of 25% (0.72 X 0.35=0.25). We anticipate another 5% reduction in total courses by decisions to withhold antimicrobials in the intervention arm, for total reduction of 30% (25% + 5% = 30%), resulting in an absolute reduction of 0.38 (0.30 X 1.26=0.38) in total courses/person years in the intervention vs. control arms.

Sample size estimates were computed using an approach for comparing rates based on a simplified assumption of a Poisson distribution for the number of antimicrobial courses. To achieve at least 90% power in testing for an absolute reduction in antimicrobial courses/person year of 0.38, we require a total of 28 NHs (14 NHs/arm), assuming each NH contributes, on average, 15 residents (total 410 residents; 205/arm) and each resident contributes, on average, 0.79 person-years based on SPREAD data. With this sample size, repeated power calculations for H1 using a more complex simulation of the negative binomial-logit hurdle model found that we will have > 90% for testing the joint effect of the intervention reducing the probability of having at least one antimicrobial course, and given any antimicrobial use, the number of courses. The sample size also provides adequate power to detect meaningful effect sizes for Aims 2 and 3. Control rates are based on prior studies; ~13% of residents will have advance care planning for infection management (documented provider-proxy discussions or new

directives to withhold antimicrobials) and experience 3.25 burdensome procedures/person-year for UTIs and LRIs.

### 2 Reporting

### 2.1 Data Flow

[name] will oversee the training of the field staff for two months prior to starting data collection. One research Assistant (RA) will be responsible for screening subjects and conducting chart reviews. To the extent possible, the RA collecting outcome data through chart reviews will be blinded to nursing home randomization. All data will be collected and entered electronically by the RA using laptop computers in the field. Electronic data capture software and programming (REDCap) will be used for these purposes. Once entered, the data will be downloaded and entered into the computer systems at HSL IFAR for cleaning, programming and analyses. The pre/post knowledge scores of providers doing the education modules in intervention NHs will be submitted to the research team by the staff at the HMS CME office using a password protected electronic computer file. Once received, HSL data management will strip the scores of subject identifiers and enter the data into the electronic data file. All staff involved in the study will receive training in the protection of human subjects.

Data management and analysis for the study will take place at Hebrew SeniorLife (HSL) under the direction of the informatics and biostatistics cores at the Institute for Aging Research (IFAR). All access to data is restricted to those on the research team who have been authorized by the PI to use this information. The HSL information technology (IT) department adheres to all the policies and practices under HIPAA regulations and is responsible for securing IFAR's IT infrastructure including physical servers and application software. IFAR has established additional sensitive data policies and procedures in concert with the IRB to ensure safe data handling by faculty and staff. In order to preserve confidentiality, subjects will be assigned a study number known only to the co-PIs, RAs and data manager. All physical documentation and IT assets are stored in a locked area at HSL, monitored 24-hours a day by security personnel, and accessible only by authorized employees. Access to the HSL cooperate computer network is strictly prohibited and all electronic research data will be stored on dedicated IFAR systems located on our private network. Access to these data will be limited to study personnel on a "need to know" basis. If a NH resident is deemed ineligible for the study, all personal health information obtained for screening purposes will be destroyed as soon as possible.

### 2.2 Report Generation

The final statistical report will describe and justify any deviations from the original statistical plan described herein. If necessary, such deviations will be treated as a protocol amendment.

The final statistical report will be accompanied by a description of the data cleaning process and will provide summaries of key findings. All programs used to produce the statistical reports will be documented, tested, and archived.

### 2.3 Definitions of Analysis Populations

Intent-to-Treat (ITT) Population:

All eligible residents enrolled into the study will be included in the ITT population. The ITT population will be the primary analysis population for all primary and secondary outcomes.

### Safety Population:

As randomization is at the level of NH, the safety population will be coincidental with the ITT population for this study.

### 3 Overview of Planned Analyses

### 3.1 Recruitment and Participant Status

Total residents over time will be summarized overall and by intervention group. The number of residents screened, enrolled, withdrawn, and completing the study will be summarized overall and by intervention group. Reasons for screen failure and dropout will be summarized overall and by intervention group.

The corresponding descriptive summaries are outlined in Appendix A, Section A.1.

### 3.2 Resident Demographics and Baseline Characteristics

Demographic and clinical characteristics of residents at baseline will be summarized by intervention arm. Resident characteristics will include measures of demographic information, health status, cognitive status, functional status, and advance care planning.

The corresponding descriptive summaries are outlined in Appendix A, Section A.2.

### 3.3 Adverse Events

The study has been granted minimal risk status by the NIH. Patients with advanced dementia are very frail. In the natural course of the disease, we expect a 40% mortality rate over one year. Thus, deaths are not considered an adverse event.

The intervention does not involve any direct treatment of residents. Treatment of suspected infections is ultimately at the discretion of the nursing home primary care provider. Nonetheless, as part of this study, every 2 months, we will be collecting data from the residents' charts about the rates of suspected urinary and respiratory infections, treatment of these infections, and appropriateness of the treatments as defined by our primary outcome.

The are no anticipated serious adverse events or adverse events in this study. Any unanticipated adverse events will be compared between intervention groups using chi-square tests or Fisher's exact tests as appropriate. The corresponding descriptive summaries are outlined in Appendix A, Section A.3.

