### **8.4.1 Control home Start-up**

Following randomization, the project director contacts the administrator to inform them of the facility's research assignment, facilitate a brief environmental scan questionnaire, and schedule a brief (30 minute) in-service for the leadership team and staff to introduce them to the study and data collection procedures. At the start of data collection, flyers informing residents and family members about the study will be posted throughout the facility.

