### **8.4.2 Intervention home Start-up**

Following randomization, the project director contacts the administrator of the intervention NH and informs them of their study assignment. She reminds him/her of the implications of the intervention assignment, asks him or her to select a site champion and facilitates completion of

the environmental scan questionnaire. Study start-up within intervention homes will involve at least 3 in-person meetings and up to weekly check-in phone calls between the research team PD and the site champion. During this time members of the TRAIN AD team will meet with members of the leadership team and site champion within the NH to review the program and intervention components and strategize about the best way to implement them within the NH. The following activities will occur during the 3 month planning period within intervention facilities:

1. Identify TRAIN-AD site champion
2. Completion of infection management questionnaire
3. Develop implementation plan with NH leadership during 3 on-site planning meetings
4. Identify targeted providers
5. Schedule training seminar
6. Provide orientation packages, conduct training seminars, and introduce on-line course to targeted providers
7. Conduct final facility set-up (e.g., hang posters of algorithms and study flyers throughout NH).

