### **11.4 Reporting Procedures**

Although, there are no anticipated adverse events, should any unanticipated study-related event of concern come to the attention of any research team member (i.e., report by site champion, proxy or provider), it will be documented on a 'event of concern' form by the PD and reviewed within 24 hours with the PI. Site champions will be trained on this procedure during the 3-month facility planning period. Any unanticipated adverse event will be promptly reported in writing to the NIH and the HSL IRB within 48 hours by the PI.

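### The between-arm adverse event test in SAP 3.3 ignores randomisation by home and rests on passive reports whose described route is stronger in intervention homes

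*SAP*

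**What the plan says.** SAP 3.3 expects "no anticipated serious adverse events or adverse events in this study", then plans a test should some occur: "Any unanticipated adverse events will be compared between intervention groups using chi-square tests", or Fisher's exact test where that suits the counts. Deaths are outside the comparison: "Thus, deaths are not considered an adverse event". SAP 3.5 specifies robust variance for clustering within homes, but only for H1, H2, H3a and H3b.

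Protocol 11.4 describes how events are found. One is recorded if it reaches a member of the research team, with the sources given as "i.e., report by site champion, proxy or provider". The only training mentioned is for champions: "Site champions will be trained on this procedure during the 3-month facility planning period".

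The start-up sections differ by arm. In intervention homes the project director contacts the administrator and "asks him or her to select a site champion" (Protocol 8.4.2). In control homes the director administers a short questionnaire and arranges to "schedule a brief (30 minute) in-service for the leadership team and staff" on the study and its data collection, and flyers are posted (Protocol 8.4.1). That section mentions neither a champion nor event reporting.

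Protocol 9.2 has deaths, hospitalisations, emergency room visits and new acute illnesses abstracted from charts every two months and at death, in both arms, but its table gives their purpose as descriptive.

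**The concern.** Two separate problems meet in one test.

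The first is ascertainment. An event enters the dataset only if somebody reports it, and several described features make a report more likely in an intervention home. Champions are trained to report. They have monthly calls with the project director (Protocol 8.5.4). Intervention proxies are mailed the director's contact details, while control proxies have only flyers (Protocol 7.3.3). Intervention providers receive information packets with contact details (Protocol 7.3.2). With equal true harm, more events could then be recorded in the intervention arm; harm in control homes could also go unrecorded.

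The second is the unit of randomisation. Homes are randomised, but a chi-square or Fisher test treats the 410 residents as independent.

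This is the only between-arm test that the SAP labels as an adverse event analysis, in a trial that aims to reduce antimicrobial starts. The Data Safety Monitor receives adverse events, with a semi-blinded sub-report by group, and may stop the study on those reports without a priori rules (SAP 1.6 and 1.7). A misleading difference, or a misleading absence of one, could therefore enter a real decision.

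**Working it through.** **The plan's own figure.** The documents give no figure for the adverse event test. Their sample size does reproduce. With the Poisson-regression method in the protocol's reference list, control rate 1.26, rate ratio 0.70, 0.79 person-years per resident, two-sided 5% and 90% power (SAP 1.8):

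N = [1.96·√4 + 1.2816·√(2 + 2/0.70)]² / (0.79 · 1.26 · (ln 0.70)²) = 359.2

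The design effect is 1 + (15 − 1)·0.01 = 1.14, and 359.2 · 1.14 = 409.5, hence 410. So the plan allows for clustering in its sample size.

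**Clustering and the adverse event test.** Mean home size is 410/28 = 14.64. The design effect is DE = 1 + 13.64·ICC, and the actual size of a nominal 5% test is about 2·(1 − Φ(1.96/√DE)). The ICC of 0.01 in SAP 1.8 is for antimicrobial courses; an ICC for adverse events is not given, so the other values are assumed.

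| ICC | DE | Approximate size | Effective residents per arm |
|---|---|---|---|
| 0.01 | 1.136 | 6.6% | 180 |
| 0.02 (assumed) | 1.273 | 8.2% | 161 |
| 0.05 (assumed) | 1.682 | 13.1% | 122 |

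A beta-binomial simulation (20,000 runs, 14 homes and 205 residents per arm) at assumed event risks of 2%, 5% and 10% gave:

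- ICC 0.01: chi-square 5.9%, 6.1%, 6.1%; Fisher 2.6%, 4.0%, 4.4%.
- ICC 0.05: chi-square 11.4%, 13.0%, 12.5%; Fisher 6.0%, 9.2%, 10.1%.

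**Unequal reporting.** Assume no true difference, full reporting in intervention homes, a stated share reported in control homes, and ICC 0.01. The apparent risk ratio is 1/share. The share of trials with p < 0.05 (chi-square / Fisher) is:

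| Share reported in control | Apparent ratio | True risk 2% | True risk 5% | True risk 10% |
|---|---|---|---|---|
| 75% | 1.33 | 7.1% / 3.1% | 10.5% / 7.1% | 15.5% / 12.3% |
| 50% | 2 | 12.8% / 5.5% | 27.3% / 19.5% | 47.9% / 42.0% |
| 25% | 4 | 26.5% / 11.8% | 60.9% / 48.9% | 89.4% / 85.6% |

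**If events are rare.** With capture of 50% in control and 90% in intervention homes (assumed) and independent residents, an exact binomial calculation gives Fisher p < 0.05 in 3.2% of trials at a true risk of 2%, 0.4% at 1% and 0.02% at 0.5%. With 205 per arm, 5 events against 0 gives p = 0.061 and 6 against 0 gives p = 0.030. Below about six events in all, Fisher's test cannot reach significance. The apparent ratio is still inflated (0.90/0.50 = 1.8), so the listing itself needs care in reading.

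**The case against.** The strongest reply is that little will turn on this test. No adverse events are anticipated, the pilot had none (Protocol 11.2), and deaths are excluded. With sparse counts Fisher's test would apply, and at the SAP's ICC its size stays below 5%. That stands, and it limits the weight of the point. False-positive rates of 20% or more in the working need true event risks of at least 2% together with severe under-reporting in control homes. A reader might take them as forecasts; the documents give no event or capture rate that would support this.

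A reader might also infer that control homes have no site champion at all. The documents point that way without saying so. Protocol 8.4.2.1 describes calls among champions of the intervention sites, and Protocol 11.2 counts the champion's burden in the intervention homes. But the opening of Protocol 8 refers to a champion in each home, Protocol 11.5 assigns event follow-up to the champion regardless of arm, and Protocol 13.1.1 and 13.2.1.1 give champions access to the resident code sheet without limiting this to one arm. Some of this wording concerns programme roll-out or booklet mailing, so it is weak evidence for control-home champions, but it leaves the matter open.

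Nor are champions the only route. Proxies and providers in both arms may report, flyers with contact details are posted in every home, and charts in both arms are reviewed every two months. The asymmetry is one of degree.

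Finally, part of the ground is already covered. Events are listed by group in Table A.3.2, and hospital transfers for suspected infection fall under H3b with robust variance. Neither supplies a between-arm comparison of deaths, all-cause hospital use or new acute illness.

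**Conclusion.** The point holds in limited form. The test in SAP 3.3 does not respect the randomisation by home, and it is applied to reports whose described route is stronger in one arm. Its p-value could not be read as evidence on harm alone, in either direction.

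The two defects should be kept apart. Ignoring clustering understates the variance; it does not bias the estimated difference, although a reader might infer that it does. At the SAP's ICC this effect is small for chi-square and absent for Fisher; it matters only if adverse events cluster more strongly, as at the assumed 0.05. Bias can come from unequal reporting, and no choice of test removes it. Its size rests on assumed event and capture rates; if events are as rare as the protocol expects, a falsely significant result is unlikely, but the test is then also nearly uninformative.

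No primary or secondary outcome is affected. The change is worth making because better safety data are already collected in the same way in both arms and are not compared.

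**What to change.** 1. In SAP 3.3, replace the between-arm test with a listing and counts by arm, and state that these are spontaneous reports with possibly unequal ascertainment. SAP 3.4 already treats unanticipated problems in this way.
2. Add a between-arm safety comparison of deaths, hospitalisations and emergency room visits, and new acute illnesses, from the chart data in Protocol 9.2, with variance clustered by home as in SAP 3.5. Report estimates with confidence intervals. Since the intervention is meant to reduce transfers for suspected infection, hospital use should be read beside H3b.
3. Reconcile the opening of Protocol 8, 11.5, 13.1.1 and 13.2.1.1 with Protocol 8.4.1, 8.4.2 and 8.4.2.1 on whether control homes have a site champion, and state who reports and follows up events there.
4. Where timing still allows, cover the event-of-concern procedure in the control-home in-service. SAP version 7.0 is dated April 2020, ten months after the revision that added the last homes, so this may no longer be possible; items 1 to 3 do not depend on it.

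The cost is SAP and protocol wording and a small amount of extra analysis, with no new data. What is given up is a formal test on spontaneous reports.
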